8.2 Screening Visit (Visit 1)

Signed informed consent must be in place before any study-related assessments are performed and may be obtained prior to the Screening Visit.

In some cases patients may be asked to attend up to 2 Screening Visits to complete all assessments at screening. In exceptional cases, the screening period (visit interval between Screening and Baseline Visits) may be extended with approval from the sponsor provided the Lundbeck medical expert accepts the rationale provided for the extension.

At the Screening Visit, the patient must be assisted with the provisioning and training of the eDiary and with training of efficacy and pharmacoeconomic assessments (PROs). Details will be provided in a separate user manual. See section 9.2.2 for further details on eDiary.

Exit Interview subset: at the Screening Visit, the patients undergoing the Visit 8 exit interviews must provide a signed subset-specific Informed Consent. Details will be provided in a separate exit interview guide. See section 9.5.1 for further details on exit interview.

8.2.1 Pre-screening

Each site must record in a pre-screening log which patients attended the Screening Visit.

Prior to the Baseline Visit, a study-specific *Eligibility Form* must be completed by the site and transmitted to the CRO for their review. A confirmation that the patient can continue further with the study procedures is required before randomization.

8.2.2 Patient Identification Card

Each patient will be provided with a patient identification card that states, at a minimum, the name of the IMP, the study number, the patient identification number, the investigator's name, and an emergency telephone number providing 24-hour service.

The patient identification card should be returned to the investigator upon completion of the patient's participation in the study.

8.2.3 Re-screening

Rescreening is only allowed for patients with a *complete* Screening Visit and who do not fulfil:

- the required duration of a washout period for a medication that is disallowed prior to screening, or,
- a stable usage period for a medication that is allowed with restrictions prior to screening.

Rescreening may also be allowed for patients with a *complete* Screening Visit but are required to be in quarantine due to a positive COVID-19 test.

The patient must already have either started the washout prior to screening or be on the allowed dosage as part of their standard clinical care. Washout or change in dosage may not be done specifically for inclusion into this study.

Authorization for re-screening may only be granted by the sponsor's medical expert (or the CRO's medical monitor) after a thorough review of all data from the original Screening Visit.

At the new Screening Visit, the patient must sign a new *Informed Consent Form*. At the new Screening Visit, the patient will be assigned a new screening number. A re-screened patient must have a *complete* new Screening Visit, and all the eligibility criteria must be re-assessed at the new Screening Visit.

The following information will also be recorded in the eCRF at the new Screening Visit:

- that the patient has previously been screened for the study
- that re-screening has been authorized by the sponsor's medical expert (or the CRO's medical monitor)
- the screening number that was assigned to the patient at the original Screening Visit

If a patient is re-screened, no data from the original Screening Visit will be used.

A patient may only be re-screened once.

8.3 Baseline Visit + IMP (Visit 2)

In exceptional cases, the screening period (visit interval between Screening and Baseline Visits) may be extended with approval from the sponsor provided the Lundbeck medical expert accepts the rationale provided for the extension.

The Baseline Visit also includes IMP administration and will occur 28-30 days after the Screening Visit. Inclusion and exclusion criteria review must be done prior to dosing at the Baseline Visit.

For procedures preceding and following IMP administration, see section 8.5.

8.4 **Primary Outcome + IMP (Visit 5)**

The Primary Outcome Visit comprises assessments of the primary, secondary and exploratory endpoints. The Primary Outcome Visit also includes IMP administration. For procedures preceding and following IMP administration, see section 8.5.

8.5 IMP Visits (Visits 2, 5, 8, 11, 14, 17)

At the IMP Visits, the infusion is preceded by assessments of vital signs including body temperature, concomitant medications, AEs, physical examination, ECG, blood and urine sampling and C-SSRS administration.

Assessments involving interviews and scales must be administered before the infusion. PROs will be completed in the clinic the following order; HIT-6, PGIC, MBS, MSQ v2.1, EQ-5D-5L, HCRU, WPAI. Alternatively, PROs which are scheduled in alignment with an IMP visit can be completed in the remote setting within 3 days prior to the scheduled clinic visit date.

Patients must complete the daily eDiary entries prior to infusion. A compliance check of the eDiary will be conducted and the patient must be assisted with re-training if necessary. See section 9.2.2 for further details on eDiary.

Patients will be monitored for at least 1 hour following end-of-infusion and before being discharged from the clinic. Patients will be requested to stay longer should the investigator determine this is clinically warranted. After the infusion, the patients will be under observation, but not confined to bed, unless the investigator decides, based on the patient's condition, that it is in the best interest of the patient to be confined to bed. Vital signs including body temperature, infusion related reactions (IRRs) and AEs will be checked after infusion and before the patient is discharged from the site. AEs should be collected prior to assessment of IRRs.

Exit Interview subset: The exit interview will be conducted at Visit 8 (Week 24 Visit or at the Withdrawal Visit for patients who withdraw prior to Week 24). The exit interview must be conducted after all visit assessments are completed. A visit window of 2 weeks is allowed for the exit interview from the last assessment conducted for Visit 8/Withdrawal Visit (for patients who withdraw prior to Week 24). See section 9.5.1 for further details on the exit interview.

8.6 Phone Contacts (Visits 3, 4, 6, 7, 9, 10, 12, 13, 15, 16, 18, 19)

The patient will be contacted via phone every 4 weeks between infusion visits for eDiary compliance check, to ensure that selected assessments have been completed and for collection of relevant information such as AEs and concomitant medication.

A compliance check of the eDiary will be conducted and the patient must be assisted with retraining if necessary. See section 9.2.2 for further details on eDiary.

Additionally, the following PROs must be completed in the remote setting in alignment with the scheduled phone contacts (see Panel 2): PGIC (at Week 4 only), HIT-6, EQ-5D-5L, HCRU, WPAI. These can be completed on the day or within 3 days prior to the scheduled phone contact date.

Only site staff trained and listed in the delegation log will conduct phone contacts and hence be allowed to call the patient. Each phone contact must be documented in medical notes and used for source data verification when completing the eCRF and for subsequent monitoring.

Phone contacts should be planned to maintain the visit schedule relative to the Baseline Visit.

8.7 **Completion Visit (Visit 20)**

Patients who complete the study will attend a Completion Visit. As the visit will be scheduled 12 weeks after the last dose of IMP, the Completion Visit will also serve as a Safety Follow-up Visit for all patients (section 8.10).

At the Completion Visit, the patient must be assisted with the closeout of the eDiary.

Patients who test positive for ADA at the Completion Visit will be asked to provide up to two additional blood samples for immunogenicity testing at 12-week intervals for up to 24 weeks.

8.8 Unscheduled Visit

An unscheduled visit may occur throughout this study if needed. Unscheduled visits can be completed if required as either site or telephone visits. At these visits clinical safety laboratory tests, ECG, vital signs can be performed. In case of any additional tests performed not covered by the existing tests specified in the protocol and the eCRF, the results can be reported in connection with an AE reporting (see chapter 10) or documented in the medical notes as applicable.

8.9 Withdrawal Visit

Patients who withdraw from the study will be asked to attend a Withdrawal Visit, if at all possible. The visit must be scheduled 12 for weeks after the last dose of IMP after withdrawal.

As the Withdrawal Visit will be scheduled 12 weeks after the last dose of IMP, this visit will also serve as a Safety Follow-up Visit for all withdrawn patients (section 8.10). Patients who withdraw prior to Week 24 will undergo additional efficacy evaluations, thus for these patients the Withdrawal Visit will also serve as an Efficacy Follow-up Visit.

At the Withdrawal Visit, the patient must be assisted with the closeout of the eDiary.

No new information will be collected from patients who withdraw from the study, except information collected in relation to the scheduled Withdrawal Visit or needed for the follow-up of adverse events (section 10.5).

The reason for withdrawal must be recorded in the eCRF.

For a patient who withdraws consent:

- if the patient withdraws consent during a visit and then agrees to it being the final visit, the investigator will complete the visit as a Withdrawal Visit and all the data collected up to and including that visit will be used
- if the patient withdraws consent during a telephone conversation, the investigator will ask the patient if they will attend a Withdrawal Visit 12 weeks after their last dose. If the patient:
 - agrees to attend a Withdrawal Visit, all the data collected up to and including that visit will be used
 - refuses to attend a Withdrawal Visit, the investigator should attempt to follow the patient's safety and future treatment; any information collected will only be recorded in the patient's medical records
- if the patient explicitly requests that the patient's data collected from the time of withdrawal of consent onwards not be used, this will be respected

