- r An unblinded pharmacist or designee is responsible for receiving, storing and preparing IMP. The pharmacist or designee will not be responsible for other aspects of the clinical trial where blinding is necessary.
- s A designated unblinded CRA is responsible for the IMP accountability.
- t Pregnancy test at Screening to be performed using serum β -HCG. At all other visits, urine pregnancy testing will be performed and in case of a positive finding, confirmatory testing will be performed via serum β -HCG.
- u Exit Interview subset: Patients undergoing the exit interviews must provide signed subset-specific Informed Consent. The exit interview will be conducted shortly (no later than 2 weeks) after the last assessment of the Week 24 Visit or Withdrawal Visit for patients who withdraw prior to Week 24. The exit interview must be conducted after all visit assessments are completed. Details will be provided in a separate exit interview guide.
- v Patients who withdraw, except for those who withdraw their consent, will be asked to attend a Withdrawal Visit 12 weeks after the last dose of IMP and undergo Safety Follow-Up evaluations. Patients who withdraw prior to Week 24 will undergo additional Efficacy Follow-Up evaluations.
- w Exploratory gene expression profiling (RNA) and metabolomics/proteomics are an integrated part of the study and are covered by the main Informed Consent.
- x Sampling for pharmacogenetics is optional and a separate signed Informed Consent must be in place to cover this analysis.
- y Whole blood samples for serum separation and potential future ADA analyses will be drawn at Week 24 and at the Completion or Withdrawal Visit.

Table of Contents

List	of Pan	els	22
List	of Abb	previations and Definitions of Terms	23
Mai	or Cha	nges Since Last Edition	26
1		luction	
	1.1	Background	30
		1.1.1 Overview	30

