16.8 Efficacy Analyses

16.8.1 General Efficacy Analysis Methodology

All the statistical tests of the efficacy endpoints will be two-sided tests based on a 5% significance level and all confidence intervals (CIs) will be two-sided 95% CIs, unless otherwise specified.

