16.8.6 Testing Strategy

The testing strategy will be a sequence of tests, either testing one endpoint at a time or using Bonferroni-Holm to test a group of endpoints. Only if one step has shown a statistically significant effect will the formal testing continue with the next step, thus ensuring protection of the type 1 error. The steps are described below.

A significance level of 0.05 will be used. The significance level is denoted by α below.

Step1

Test the primary endpoint change from baseline in MMDs (Weeks 1-12) for the 300 mg dose compared to placebo on a significance level of α . Only if the p-value $<\alpha$ in favour of the 300 mg dose is the effect considered statistically significant and the testing continues with the next step.

Step 2

Test the key secondary endpoint 50% responders for MMD (Weeks 1-12) for the 300 mg dose compared to placebo, using a significance level of α . Only if the p-value $<\alpha$ in favour of the

300 mg dose is the effect considered statistically significant and the testing continues with the next step.

Step 3

Test the primary endpoint change from baseline in MMDs (Weeks 1-12) for the 100 mg dose compared to placebo on a significance level of α . Only if the p-value $<\alpha$ in favour of the 100 mg dose is the effect considered statistically significant and the testing continues with the next step.

Step 4

Test the key secondary endpoint 50% responders for MMD (Weeks 1-12) for the 100 mg dose compared to placebo, using a significance level of α . Only if the p-value $<\alpha$ in favour of the 100 mg dose is the effect considered statistically significant and the testing continues with the next step.

Step 5

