The patient will receive IMP starting from the Baseline Visit to follow a dosing schedule with IV infusions every 12 weeks with either eptinezumab or placebo over 30 minutes (+15).

At Visit 8 patients will enter the Extension Period. Patients who were assigned to placebo in the Placebo-controlled Period will be randomly allocated to one of two treatment groups: eptinezumab 300 mg or eptinezumab 100 mg with a ratio of 1:1. Patients assigned to eptinezumab 300 mg or eptinezumab 100 mg in the Placebo-controlled Period will continue on their original assignments.

An overview of the study is presented in Panel 2 and the scheduled study procedures and assessments are summarized in Appendix II. See also the *Clinical Study Protocol* for further details on the study design.

Panel 2 Study Design

For patients who withdraw, except for those who withdraw their consent, a Withdrawal Visit will be scheduled 12 weeks after the last dose of IMP. The withdrawal visit will include Safety Follow-up evaluations and will therefore also serve as a Safety Follow-up Visit.

For patients who withdraw prior to Week 24 the Withdrawal Visit will allow for eDiary closeout and for a final assessment of scales not based on the eDiary. Patients are expected to complete their eDiary until this Withdrawal Visit unless the patient withdraws consent.

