7.2 Withdrawals

For each period, the number of patients who withdrew from treatment, which also implies that they withdrew from the study, will be summarized by treatment group, and primary reason for withdrawal, and by treatment group and all reasons for withdrawal.

Patients who withdrew will be listed for each period. The listings will include the number of days in the study until withdrawal, the date of first IMP infusion, the date of the latest IMP infusion prior to withdrawal, the number of days since latest IMP infusion, the primary reason for withdrawal, all reasons for withdrawal, specification of 'Other' reason, and a flag if the drug code was broken. For the listing for the Extension Period both date of first IMP in the Placebo-controlled Period and date of first IMP in the Extension Period will be included.

If needed, a listing of patients who withdrew due to COVID-19 situation (as the primary reason) will be provided for each period as well as a listing of patients withdrawing due to falling ill of COVID-19 (as the primary reason). The latter is defined as patients withdrawing due to an adverse event, which is then specified to be COVID-19.

If relevant, Kaplan-Meier failure plots of time to withdrawal in each period will be presented by treatment group. The time will be calculated from the date of first dose of IMP in the period to the date of completion or withdrawal. Patients who completed the period will be regarded as censored. For the Extension Period, the plot will be by treatment sequence group. All tables, graphs, and listings will be based on the APTS for the Placebo-controlled Period and on APTS_LT for the Extension Period.

8 Demographics and Baseline Characteristics

Demographics (sex, age, age group, race, ethnicity, region, country); baseline characteristics (height, weight, and BMI); baseline disease characteristics; and baseline efficacy variables will be summarized for the Placebo-controlled Period by treatment group.

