It is hypothesised that patients withdrawing very early in the study (during the first 4 weeks after first IMP infusion) due to adverse events have not been successfully treated. Therefore, in a situation where a patient withdraws during the first 4 weeks after first IMP infusion and the amount of data collected through the eDiary is not sufficient to derive a monthly score using the general derivation rules, the missing data is penalized to reflect that the symptom level will be close to the expected higher level of MMDs that was experienced at Baseline.

Patients withdrawing due to adverse events later in the study are hypothesised to behave similarly to the study population as a whole.

Details of the imputations used can be seen in the rules for handling missing data described in Section 19.1.1.

Withdrawal due to other reasons

Withdrawals due to other reasons than lack of efficacy or adverse events will be handled with a treatment policy strategy using the data collected regardless of the intercurrent event and using the imputation rules specified in Section 19.1.1.

Interruption/termination of infusions

If interruption or termination of infusion leads to withdrawal, it is handled according to the rules above.

Temporary interruption of infusion is not expected to impact the efficacy data. Premature termination of infusion (that is, only receiving a partial infusion) could impact the efficacy. However, it is expected that the implications of a partial infusion will be reflected in the collected eDiary data.

Hence, the intercurrent events of temporary infusion interruptions, premature terminations of infusions, and complete termination of infusions not leading to withdrawal will be addressed using a treatment policy strategy by using the data collected regardless of these intercurrent events.

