12.4 Analysis Methodology for the Key Secondary Endpoints

12.4.1 Key Secondary Estimands

The key secondary endpoints 50% response (Weeks 1-12), 75% response (Weeks 1-12), and change from baseline in MMDs (Weeks 13-24) are all derived based on the number of MMDs for the relevant intervals.

Therefore, the key secondary estimands can be formulated similarly to the primary estimand described in Section 12.3.1, with the following modifications in regards to endpoint and population-level summary attributes. The binary 50% and 75% response variables across three 4-week intervals are calculated based on the available monthly values. Further details on the derivation of the endpoints can be found in Section 19.1.1.

50% response (Weeks 1-12)

- The **endpoint** to be obtained is a binary response variable indicating a successful response if a patient has achieved a 50% reduction or more in number of MMDs across weeks 1-12
- The **population-level summary** is the odds ratio of a successful response between eptinezumab and placebo

75% response (Weeks 1-12)

- The **endpoint** to be obtained is a binary response variable indicating a successful response if a patient has achieved a 75% reduction or more in number of MMDs across weeks 1-12
- The **population-level summary** is the odds ratio of a successful response between eptinezumab and placebo

Change from baseline in MMDs (Weeks 13-24)

• The endpoint to be obtained is the change from baseline in MMDs across weeks 13-24

• The **population-level summary** is the least squares mean difference between eptinezumab and placebo for the endpoint

Change from Baseline in HIT-6

For HIT-6, some of the intercurrent events will be addressed using different strategies than what is described for the primary and other key secondary estimands. Therefore, the phrasing of the key secondary estimand related to this endpoint is also a little different.

The differences to the strategies used for the primary and other key secondary estimands in the handling of intercurrent events are as follows:

- *Use of acute medication to treat a headache:* Instead of a hypothetical strategy, this intercurrent event will be handled using a treatment policy strategy, i.e. the values of HIT-6 are used regardless of whether the patient took any acute medication because they believed they were experiencing a migraine

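### Patients who leave before the second infusion have no usable Weeks 13-24 migraine-day data, so the treatment-policy strategy that the SAP names for other-reason withdrawals cannot be carried out for that key secondary endpoint

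*Protocol*

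**What the plan says.** **Collection.** SAP 7.2 tabulates "the number of patients who withdrew from treatment, which also implies that they withdrew from the study". Protocol 8.9 and SAP section 2 set the Withdrawal Visit 12 weeks after the last dose, and the eDiary is closed there. Protocol 8.9 adds "No new information will be collected from patients who withdraw from the study, except information collected in relation to the scheduled Withdrawal Visit", with adverse-event follow-up as the only other exception. SAP section 2 is more explicit about the diary: "Patients are expected to complete their eDiary until this Withdrawal Visit unless the patient withdraws consent".

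**Strategy.** For withdrawals not attributed to lack of efficacy or an adverse event, SAP 12.3.3 says they "will be handled with a treatment policy strategy using the data collected regardless of the intercurrent event". SAP 12.4.1 then says "the key secondary estimands can be formulated similarly to the primary estimand described in Section 12.3.1", changing only the endpoint and the summary measure. This covers the change in monthly migraine days (MMDs) over Weeks 13-24, which is tested in Steps 5 and 6 of the testing strategy.

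**Missing months and sensitivity.** SAP 19.1.1.1 and Panel 5 set any month after Week 4 with fewer than 14 diary days to missing. SAP 12.4.4 gives MMDs Weeks 13-24 one sensitivity analysis, and it alters only the Weeks 1-4 values. Placebo-based multiple imputation is planned for HIT-6 alone.

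**The concern.** A treatment-policy strategy needs outcomes observed after the event. Here the event ends observation before the endpoint window opens. The SAP names one strategy for Weeks 13-24, and the analysis delivers another.

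What is at stake is the meaning of a key secondary result under type 1 error control. For other-reason withdrawals before the second infusion, the Weeks 13-24 estimate answers what would have happened had these patients stayed. It does not answer what happened after they left. If benefit fades off drug, that favours the active arms. A reader of the report would have no planned analysis showing how much depends on this.

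**Working it through.** **1. Visit timing.** Inputs: doses at Weeks 0 and 12; Withdrawal Visit 12 weeks after the last dose, window +2 days (Protocol Panel 2); 14-day minimum per month (SAP 19.1.1.1).

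| Last dose | Diary closed | Diary days in Weeks 13-24 | Evaluable months |
|---|---|---|---|
| Week 0 | Week 0 + 12 = Week 12 (+2 days) | 0 to 2 of 84 | 0 of 3 |
| Week 12 | Week 12 + 12 = Week 24 | 84 of 84 planned | 3 of 3 |

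The gap is confined to patients who leave before the second infusion. For those withdrawing before Visit 5, SAP 19.2.1 assigns the Withdrawal Visit scales to Visit 5, so Week 24 HIT-6 is missing too.

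**2. Strategy by withdrawal reason (SAP 12.3.3, carried over by 12.4.1).**

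| Reason | Stated handling | Data in Weeks 13-24 if only one dose was given |
|---|---|---|
| Lack of efficacy | Hypothetical; the stated assumption is tied to the first 12 weeks after the first dose | None |
| Adverse event | Penalty for sparse data in the first 4 weeks; later withdrawals assumed to resemble the whole study population | None |
| Other | Treatment policy | None |

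Only the last row names a strategy that the design cannot deliver.

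**3. The plan's own figure.** Inputs from Protocol 16.10: EM effects 0.69 (100 mg) and 1.11 (300 mg), SD 3.1; CM effects 2.03 and 2.60, SD 5.8; 40% EM and 60% CM; 280 per arm, 2% without a post-baseline value. On the test level: "A significance level of 0.05 will be used" (Protocol 16.8.6), two-sided (Protocol 16.8.1).

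- 100 mg effect: 0.4 × 0.69 + 0.6 × 2.03 = 1.494 days
- 300 mg effect: 0.4 × 1.11 + 0.6 × 2.60 = 2.004 days
- SD: √(0.4 × 3.1² + 0.6 × 5.8²) = 4.902
- n per arm: 280 × 0.98 = 274.4

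Power for the primary endpoint is 94.6% by formula and 94.3% by simulation for 100 mg (stated: about 94%). For 300 mg it is 99.8% and 99.7% (stated: 99%). The plan's figures reproduce. The 68% and 58% for the key secondary endpoints cannot be checked, because their inputs are not given.

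**4. Size of the mismatch.** Let d be the full effect, w the share leaving before the second infusion (the same in each arm) and r the share of the effect kept off treatment. The documents give neither w nor r. Assume also that the Weeks 13-24 effect and SD equal the primary inputs, and that leavers resembled other patients in their arm until they left. Then

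overstatement = d × w × (1 − r).

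| w | Patients per arm | 100 mg, r = 0 | 300 mg, r = 0 | Either dose, r = 1 |
|---|---|---|---|---|
| 2% | 280 × 0.02 = 5.6 | 1.494 × 0.02 = 0.030 | 2.004 × 0.02 = 0.040 | 0 |
| 5% | 14 | 0.075 | 0.100 | 0 |
| 10% | 28 | 0.149 | 0.200 | 0 |

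These rows count every early leaver. If a share s of them left for other reasons, the part due to the mismatch is s times the figure. With s = one half (an illustration), the 10% row becomes 0.5 × 0.149 = 0.075 and 0.5 × 0.200 = 0.100 days.

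**5. What full follow-up would do to power for Weeks 13-24, 100 mg, w = 10%.**

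| Level | Current plan | Full follow-up, r = 0 | Full follow-up, r = 1 |
|---|---|---|---|
| 0.05 | 92.3% | 89.5% | 94.6% |
| 0.05/3 (first Bonferroni-Holm test) | 84.0% | 79.4% | 88.0% |

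For 300 mg, power is at least 97% throughout.

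**The case against.** The strongest reply is that the SAP never promises, for migraine days, an effect regardless of all withdrawals. That is right. A reader might infer such a promise, but SAP 12.3.1 and 12.3.3 state separate assumptions for lack of efficacy and adverse events. The wording that disregards both kinds of withdrawal belongs to the HIT-6 estimand in SAP 12.4.1. The mismatch is therefore limited to other-reason withdrawals.

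It can also be said that the model does not simply put leavers on their arm's average course. With an unstructured covariance it conditions on each patient's own earlier months. That stands, and it softens the bias where leavers were already doing worse, but it still assumes missing-at-random. Nor could any design recover everyone: some other-reason withdrawals are lost to follow-up or withdraw consent.

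Two further readings are tempting but not supported:

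- **The sentence in Protocol 8.9 costs the primary endpoint its diary data between withdrawal and Week 12.** Protocol 3.1, 8.1 and 9.2.2 all require the daily diary until the Withdrawal Visit, 8.9 itself places closeout there, and SAP section 2 agrees. The sentence is out of line and should be aligned, but a loss is not shown.
- **HIT-6 is wrongly dropped for Extension withdrawals**, because Panel 2 footnote v says "Patients who withdraw prior to Week 24 will undergo additional Efficacy Follow-Up evaluations" and offers nothing later. SAP 12.5 plans no treatment comparisons after Week 24, so no comparative conclusion depends on it.

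Finally, the change summary in Protocol Edition 3.0 treats the Placebo-controlled Period as complete and describes sponsor staff as unblinded after its lock. Extending collection may no longer be possible. This limits the remedy but does not remove the mismatch.

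**Conclusion.** The point holds in limited form. Patients withdrawn before the second infusion have no evaluable MMD month in Weeks 13-24. For other-reason withdrawals among them, the stated treatment-policy strategy is in effect a hypothetical one, and no planned sensitivity analysis for this endpoint examines it.

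Under the assumptions in the working, the overstatement is at most 0.03-0.15 days for 100 mg and 0.04-0.20 days for 300 mg at 2-10% early leaving. It is smaller when only other-reason withdrawals are counted and zero if the effect persists off drug. The range rests on rates and an off-treatment effect that the documents do not give.

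The primary endpoint and Week 12 HIT-6 are not touched by this gap, because planned collection reaches Week 12. It should not be read as showing that the stated power or sample size is wrong.

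A related inconsistency also needs settling. SAP 7.2 equates leaving treatment with leaving the study, while SAP 12.3.3 provides for patients whose infusions end for good without withdrawal.

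**What to change.** 1. **Where collection is still open:** continue the eDiary and the remote HIT-6 to Week 24 after study drug stops, unless consent is withdrawn, and use these data in the Weeks 13-24 and Week 24 analyses. The cost is a protocol and SAP amendment, some diary burden for the few patients concerned, and possibly a smaller estimated effect.
2. **Otherwise:** restate SAP 12.4.1 so that Weeks 13-24 for patients leaving before the second infusion are handled by a hypothetical strategy. Add a placebo-based imputation analysis of MMDs Weeks 13-24, modelled on the one planned for HIT-6 in SAP 12.4.4 and Appendix IV. Label it post hoc if unblinding has occurred. The cost is wording plus one analysis whose code largely exists.
3. **In either case:** reconcile SAP 7.2 with the provision in SAP 12.3.3 for infusions ended without withdrawal, and align the sentence on new information in Protocol 8.9 with Protocol 9.2.2 and SAP section 2.

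None of this changes when treatment stops.
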